- Section 5.5.11 Discontinuation of study treatment: Updated language to define withdrawal of consent and clarify process of discontinuation
- Section 5.5.12 Withdrawal of Consent: Added section to clarify Withdrawal of Consent procedures
- Section 5.5.13 Lost to Follow-Up: Updated template language regarding patients lost to follow-up

[figure not shown]
- Section 5.5.14 Early Study Termination: Updated template language for clarification
- Section 6: Removed “premature” to clarify study discontinuation

Changes to specific sections of the protocol are shown in the track changes version of the protocol using ~~strike through red font for deletions~~ and red underlined for insertions.

IRB/IEC

A copy of this amended protocol will be sent to the Institutional Review Boards (IRBs), Independent Ethics Committees (IECs) and Health Authorities.

The changes described in this amended protocol require IRB/IEC approval prior to implementation. In addition, if the changes herein affect the Informed Consent, sites are required to update and submit for approval a revised Informed Consent that takes into account the changes described in this amended protocol.

Amendment 6

As of 01 March 2014, 19 patients have been enrolled under protocol Amendment 4 of the protocol. A total of 17 patients completed the 22 week core phase of the study and 2 patients were discontinued. Of the 17 patients who completed the core phase, 16 patients are enrolled in the optional long term extension-1 of the study.

Amendment Rationale

The purpose of this protocol amendment is to continue the study to monitor patients for long-term safety and efficacy, and to provide continued access to LCI699 to patients who have completed long term extension-1. As there are only 16 patients currently participating in extension-1, and the clinical development program of LCI699 is still in its early stage, it is important to continue to collect long-term safety and efficacy data over a longer period of time. In addition, considering that currently available alternative treatment options have limitations to their efficacy and safety profiles, this additional extension (extension-2) will provide patients who are clinically benefitting from LCI699 an opportunity to continue to have access to the drug until LCI699 is commercially available and reimbursed or through the availability of a local access program.

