At Day 154, patients have the option to enter the 12 month extension phase at the investigators discretion provided they do not meet any discontinuation criteria. Dosing titration during the extension is to be based on efficacy (UFC control) and safety ([Section 5.5.4](#)). Patients will come in for monthly visits for the first 6 months (Day 154- Day 322) of the long-term extension and then will have visits every 3 months from month 6 through 12 (Day 322 - Day 490). At the end of the extension phase, patients will complete an End of Treatment-Extension visit at Day 490 and an End of Study visit 28 days after the last dose administration, if not continuing into long term Extension-2.

Optional long term extension-2

At Day 490, patients have the option to enter a second long term extension phase (extension-2) at the investigator's discretion, provided they do not meet any of the study discontinuation criteria. Dose adjustment during the extension is to be based on efficacy (UFC control) and safety ([Section 5.5.4](#)). Patients will come in for visits every 3 months during the first 18 months of extension-2 (approximately 3 years into the study), and every 6 months thereafter. This additional long term extension (extension-2) will provide important long term safety and efficacy data of LCI699 in patients with Cushing's disease.

1. Patient treatment in Long Term Extension-2 will end at each site within 4 months after a separate roll-over study is opened at their site, or by 31 December 2019 (whichever occurs

earlier). The roll-over study will provide an opportunity of continued treatment for patients who are still ongoing at that time and who are clinically benefitting from LCI699. For sites where a separate roll-over study is not an option, the patient may be offered a local alternative treatment option.

Patients entering the roll-over protocol will complete an EOT visit. For these patients the EOS visit is not applicable, as treatment on LCI699 will not be interrupted. Sites with the separate roll-over study option available, should arrange their patient's End of Treatment (EOT) visit within 4 months of the roll-over study being opened at their site (i.e. earlier than the 6 month visit intervals in Long-Term Extension-2), to allow their patients to continue their LCI699 dose on this new study.

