3.5 Risk/ benefit for this study

Potential benefits

Biochemical remission is a goal in the treatment of Cushing's disease. Preliminary data from this PoC study in patients with Cushing's disease clearly demonstrated that LCI699 can reduce and normalize plasma cortisol in this population. However, it is unknown whether patients responding to LCI699 will eventually loose UFC control. Patients will be discontinued from LCI699 treatment in case of unsatisfactory response.

The primary treatment and standard of care for Cushing's disease is surgical removal of the pituitary tumor via transsphenoidal adenectomy. Therefore, in order to avoid any potential delay in receiving first line treatment patients enrolled under [Amendment 4](#) should have either failed standard therapy (including surgery) or can be de novo patients for whom surgery is not an option. Given LCI699's potency to suppress cortisol synthesis, it is conceivable that patients may ameliorate some of the sequelae of their hypercortisolism state while on the drug for the planned duration of this study protocol following [Amendment 4](#). Patients who are responding to LCI699 with good tolerability have the option to participate in optional two long term extension phases of the study.

Potential risks

Based on the preclinical and clinical experience with LCI699 the risks associated with this study are outlined below. The risks to patients will be minimized by strict inclusion/exclusion criteria, close clinical monitoring and predefined dose adjustment and dose termination criteria (see [Section 5.5.4](#) and [Section 5.5.9](#)).

Effects on QTc interval

Final results from the completed ICH E14-compliant thorough QT Study LCI699C2105 showed that the predicted mean QT effect of osilodrostat was below the threshold of regulatory concern for the currently investigated dose range (2-30 mg twice a day [bid]).

Effects on blood pressure

LCI699 has been shown to reduce BP of hypertensive patients in a dose dependent manner over 4-8 weeks. An acute decrease in BP has not been observed with LCI699 in healthy volunteers (up to 200 mg) or hypertensive patients (range tested = 0.25 mg - 2 mg/day). Doses used in this study will be higher than those where a BP effect was observed, and may therefore elicit larger decreases in BP than observed to-date. Patients with Cushing's disease have a high prevalence of hypertension and effective treatment of hypercortisolism may result in reductions in blood pressure.

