### 7.3.2 Secondary efficacy analysis

#### 7.3.2.1 Week 22 treatment effect

As mentioned in Section 3, the Week 22 treatment effect of LCI699 has already been reported in a CSR.

Similar analyses to those performed for the Week 22 treatment effect will be performed for scheduled assessment time points during the extension periods of the study.

A patient is considered to be a responder at a particular time point if the mean UFC level (at least two 24-hour measurements) at that time point is  $\leq$  ULN or represents a  $\geq$  50% decrease from baseline. Patients who discontinue for a disease or treatment related reason (e.g. death, adverse event, clinical disease progression etc.), or whose mean UFC levels are higher than the normal limit and experience  $<$  50% decrease in UFC are classified as non-responders or uncontrolled. If mUFC is missing at a particular time point, then the value will not be imputed but the patient will be considered a non-responder at that time point.

The denominator for the response rate calculation is the number of patients in the safety analysis set for weeks 10 and 22, which is the core phase. For time points after the core phase, the denominator will exclude patients who did not enter the extension phase. Patients who discontinued due to administrative reasons will also not be included in the denominator of any time points after the time of their discontinuation. In addition, patients who are ongoing without reaching the analysis time point will also be excluded. Early discontinued patients (including those discontinuing in the core phase) will be considered as non-responders for all time points after discontinuation.

As a supportive analysis, the response rate will be calculated using only the number of observed mUFC samples at each time point. Patients who have discontinued prior to the assessment time

point, or who are ongoing but do not have a valid mUFC value, will not be counted in the denominator.

The proportion of responders and the associated two-sided 95% confidence interval will be estimated using the exact method.

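### After Week 22 the SAP drops every patient who did not enter the extension, so the long-term response rate can rise by selection, and its rule for core discontinuers conflicts with that exclusion

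*Protocol*

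**What the plan says.** **Who enters the extensions.** Protocol Section 3.1 says, for the end of the core phase, that "patients have the option to enter the 12 month extension phase at the investigators discretion provided they do not meet any discontinuation criteria", and for the second extension that "patients have the option to enter a second long term extension phase (extension-2) at the investigator's discretion", again provided no discontinuation criterion is met. The discontinuation list in Section 5.5.11 does not include lack of response. Section 3.5 (potential benefits) puts it differently: "Patients who are responding to LCI699 with good tolerability have the option to participate in optional two long term extension phases of the study". The same section adds: "Patients will be discontinued from LCI699 treatment in case of unsatisfactory response". Section 5.5.7 likewise says that non-responders should be withdrawn. The Amendment 4 rationale describes the first extension as an opportunity for patients who respond, after an evaluation of benefit at Week 22.

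**Who is counted.** SAP 7.3.2.1 uses the safety set at Weeks 10 and 22. It continues: "For time points after the core phase, the denominator will exclude patients who did not enter the extension phase". Patients who stopped for administrative reasons, and ongoing patients who have not reached the visit, are also removed. Then: "Early discontinued patients (including those discontinuing in the core phase) will be considered as non-responders" at all later time points. A supportive rate uses only observed mean UFC values. SAP 7.1.2 lists core completers who did not enter the extension separately from discontinued patients.

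**How the rates will be used.** SAP Section 3 makes long-term safety and efficacy the focus of the Final CSR. SAP 3.2 extends the Week 22 UFC objective over the whole study.

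**The concern.** The same clinical outcome is handled in two ways. A patient who fails and is stopped before Week 22 stays in the long-term denominator as a non-responder. A patient who fails, completes Week 22 and does not continue is removed. The decision to continue depends on the investigator's view of benefit under either protocol wording, so removal is plausibly related to outcome. For discontinuers the SAP separates administrative from other reasons; for non-entrants it does not.

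Because the core and extension rates are presented as one series, a step up after Week 22 could be read as better or more durable control when only the denominator has changed. No planned output would show this. The observed-case rate leaves out the same patients, and the disposition table counts non-entrants without giving their reason or response status.

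**Working it through.** **1. The plan's own figures.** The documents give no long-term response rate. The nearest stated figure is in SAP Table 4-1: 12 of 15, shown as 80 (52, 96). Clopper-Pearson limits (SAP 8.7) give 80.0% (51.9, 95.7), which agrees. The rest of the table agrees to rounding, apart from one cell that has no bearing here (2 of 14: lower limit printed 0.2, computed 1.8).

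**2. Inputs.** From the protocol's summary of Amendment 6: 19 patients enrolled under Amendment 4, 17 completed the core phase, 2 were discontinued, and "Of the 17 patients who completed the core phase, 16 patients are enrolled in the optional long term extension-1". So 17 − 16 = 1 completer had not entered.

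Assumptions, not in the documents:
- all 19 were treated;
- 15 responded at Week 22;
- neither core discontinuer left for administrative reasons;
- each entrant has the same response at the first extension visit as at Week 22.

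**3. Week 22.** 15/19 = 78.9% (54.4, 93.9). The two discontinuers are non-responders.

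**4. First extension visit under the SAP.** No patient's response changes; only the denominator does.

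| Denominator | Non-entrant was a failure | Non-entrant was a responder |
|---|---|---|
| 16 entrants + 2 core discontinuers = 18 | 15/18 = 83.3% (58.6, 96.4) | 14/18 = 77.8% (52.4, 93.6) |
| 16 entrants only | 15/16 = 93.8% (69.8, 99.8) | 14/16 = 87.5% (61.7, 98.4) |

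Both rows can be drawn from SAP 7.3.2.1. The core discontinuers did not enter the extension, so the exclusion sentence removes them; the sentence on early discontinuers keeps them.

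**5. Range over the assumed number of responders, r, with denominator 18.**
- Non-entrant a failure: r/18 − r/19 = r/342. For r = 10 this is +2.9 points (52.6% to 55.6%); for r = 16 it is +4.7 points (84.2% to 88.9%).
- Non-entrant a responder: (r − 1)/18 − r/19 = (r − 19)/342. For r = 15 this is −4/342 = −1.2 points.

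**6. The supportive analysis.** It counts observed values only, so at this visit it has at most the 16 entrants: 15/16 if all have a valid value and the non-entrant was a failure. It does not restore the non-entrant.

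**7. The second extension.** SAP 7.3.2.1 and 7.1.2 refer to one extension phase. The amendment summaries show 16 patients in extension-1 as of March 2014 and 12 ongoing in November 2015. They do not say how many of the other four, if any, completed extension-1 without entering extension-2, and the SAP does not say how such a patient is counted.

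**The case against.** Restricting long-term rates to patients who went on is an openly stated choice in an exploratory, single-arm study with no long-term hypothesis test. A failure at Week 22 still counts in the Week 22 rate, and the number of non-entrants appears in the disposition table. At most one patient is affected on entry to extension-1, against exact intervals about 40 points wide. A programmer would probably take the core-discontinuer sentence as the more specific rule and arrive at 18.

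Much of this stands. It limits the size of the problem and argues for a sensitivity analysis rather than replacing the planned rate. It does not remove the inconsistency, because no planned analysis keeps a non-entering failure in the long-term denominator.

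A reader might infer three stronger things that the documents do not support:
- **That Section 3.5 reserves the extensions for responders.** It is risk/benefit narrative without the word *only*, beside the design text in Section 3.1, where response is not a condition of entry.
- **That every Week 22 failure drops out.** Such a patient may enter under Section 3.1 and then stays in the denominator.
- **That the rate is raised by a fixed amount at every later visit.** The other exclusions in SAP 7.3.2.1 change the denominator from visit to visit, and the numerator changes too. Only the first extension visit can be illustrated.

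**Conclusion.** The concern holds as a risk of selection, not as a demonstrated bias. SAP 7.3.2.1 removes non-entrants regardless of response, entry is linked to perceived benefit, and the observed-case analysis does not compensate. The long-term rate can therefore rise with no change in any patient.

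With the 18-patient denominator and 10 to 16 responders assumed, the rise at the first extension visit is 2.9 to 4.7 points if the one non-entrant was a failure. The documents give neither that patient's response nor the reason for not entering. If the patient was a responder, the rate falls slightly (78.9% to 77.8% with 15 responders).

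The unresolved handling of the two core discontinuers matters more: with 15 responders among the entrants, the same data give 83.3% or 93.8%. Treatment of patients who complete extension-1 and do not enter extension-2 is undefined.

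**What to change.** In SAP 7.3.2.1:

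- State that the non-entry exclusion applies only to core completers, so core discontinuers remain as non-responders, subject to the existing administrative-reason rule. Say how the exclusion applies to extension-1 and extension-2 separately.
- Add a sensitivity response rate for extension time points that keeps non-entrants in the denominator. Count those not in response at their last visit (Week 22, or Week 70 for extension-2) as non-responders, and state in advance how a non-entrant who was in response is counted. If the one non-entrant was a failure, the illustration returns to 15/19 = 78.9%.
- Show the number of non-entrants and their last response status beside each long-term denominator. Response status is the workable basis, because the disposition plan in SAP 7.1.2 does not list a reason for non-entry.

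In the protocol, the descriptions of extension entry in Sections 3.1 and 3.5 must be reconciled; which rule should apply is for the sponsor to settle.

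The cost is a little more programming and a possibly less favourable long-term rate. No new data collection is needed.

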3.6 Purpose and timing of interim analyses/design adaptations

[figure not shown]
Because this is an open label study, response to the therapy will be monitored as the study proceeds. In addition, an interim analysis will be performed after the first 12 patients complete 10 weeks of treatment and a CSR will be generated from this data. Additional interim analyses may be conducted for the expansion cohort and the core-PoC follow-up cohort.

4 Population

The study population will be comprised of male and female patients with endogenous hypercortisolism due to increased ACTH production from the pituitary (Cushing's disease). Approximately 15 patients (not previously enrolled in the trial) with Cushing's disease will be enrolled to participate in the study (expansion cohort). At least 8 patients are expected to complete the study. Patients who previously completed the trial prior to [Amendment 4](#) and benefited from the treatment with LCI699 will also be allowed to re-enter the study (core PoC follow-up cohort). These patients will start the study over again at screening.

The investigator must ensure that all patients being considered for the study meet the following eligibility criteria. No additional exclusions should be applied by the investigator, in order that the study population will be representative of all eligible patients.

Patient selection is to be established by checking through all inclusion/exclusion criteria at screening and study baseline. A relevant record (e.g. checklist) must be stored with the source documentation at the study site.

Deviation from **any** entry criterion excludes a patient from enrollment into the study.

4.1 Inclusion criteria

Patients eligible for inclusion in this study have to fulfill **all** of the following criteria at the screening or baseline visit as described in the [Assessment Schedules](#):

1. Written informed consent must be obtained before any assessment is performed.
2. Male or female patients aged 18 - 75 years
3. Patients must have **confirmed** Cushing's Disease that is persistent or recurrent as evidenced by:
 - UFC >1.5XULN (Mean value of three 24-hour urine samples collected within 14 days) [For Patients who completed the first 10 weeks of treatment prior to [Amendment 4](#) (Core PoC follow-up cohort), the appropriate washout of medical treatment for Cushing's disease has to be followed per inclusion criteria 5. These patients must have UFC >1 X ULN (Mean value of three 24-hour urine samples collected within 14 days).]
 - Morning plasma ACTH above lower limit of normal
 - Confirmation of pituitary origin of excess ACTH by at least one of the following three:
 1. History of MRI confirmation of pituitary adenoma (greater than or equal to 6 mm) with positive dynamic test (e.g. CRH or high dose dexamethasone suppression test)or
 2. History of inferior petrosal sinus sampling in patients with a tumor less than 6 mm that meet any of the following criteria with either CRH or DDAVP (desmopressin) stimulation:
 - Central to peripheral ACTH ratio ≥ 2 at pre-stimulation baseline, or
 - Central to peripheral ACTH ratio ≥ 3 after CRH stimulation.or
 3. Prior pituitary surgery with histopathology confirming an ACTH staining adenoma
 - Patients are permitted to washout current drug therapy to meet these entry criteria if they have a known diagnosis of Cushing's disease
4. Patients with de novo Cushing's disease can be included only if they are not considered candidate for surgery (e.g. poor surgical candidates, surgically unapproachable tumors, patients who refuse to have surgical treatment or surgical treatment is not available)
5. For patients on medical treatment for Cushing's disease the following washout periods must be completed before baseline efficacy assessments are performed
 - Inhibitors of steroidogenesis (ketoconazole, metyrapone): 1 week
 - Dopamine agonists (bromocriptine, cabergoline), PPAR-gamma agonists (rosiglitazone, pioglitazone): 4 weeks
 - Octreotide LAR, Pasireotide LAR and Lanreotide autogel: 8 weeks
 - Mifepristone, Lanreotide SR: 4 weeks
 - Octreotide and Pasireotide (immediate release formulation): 1 week
 - Other experimental therapy: at least 5 half-lives

4.2 Exclusion criteria

Patients fulfilling **any** of the following criteria are not eligible for inclusion in this study:

1. Use of other investigational drugs at the time of enrollment, or within 30 days or 5 half-lives of enrollment, whichever is longer; or longer if required by local regulations, and for any other limitation of participation in an investigational trial based on local regulations.
2. History of hypersensitivity to any of the study drugs or to drugs of similar chemical classes.
3. History of malignancy of any organ system (other than localized basal cell carcinoma of the skin), treated or untreated, within the past 5 years, regardless of whether there is evidence of local recurrence or metastases.
4. Pregnant or nursing (lactating) women.
5. Women of child-bearing potential, defined as all women physiologically capable of becoming pregnant, **unless** they are using highly effective methods of contraception during dosing and for 1 week after completion of dosing. **Highly effective contraception methods include:**
 - Total abstinence (when this is in line with the preferred and usual lifestyle of the subject. Periodic abstinence (e.g., calendar, ovulation, symptothermal, post-ovulation methods) and withdrawal are not acceptable methods of contraception.
 - Female sterilization (have had surgical bilateral oophorectomy with or without hysterectomy) or tubal ligation at least six weeks before taking study treatment. In case of oophorectomy alone, only when the reproductive status of the woman has been confirmed by follow up hormone level assessment.
 - Male sterilization (at least 6 months prior to screening). For female subjects on the study the vasectomized male partner should be the sole partner for that subject.
 - Combination of any two of the following (a+b or a+c, or b+c):
 - a. Use of oral, injected or implanted hormonal methods of contraception or other forms of hormonal contraception that have comparable efficacy (failure rate <1%), for example hormone vaginal ring or transdermal hormone contraception
 - b. Placement of an intrauterine device (IUD) or intrauterine system (IUS)
 - c. Barrier methods of contraception: Condom or Occlusive cap (diaphragm or cervical/vault caps) with spermicidal foam/gel/film/cream/vaginal suppository,
 - d. In case of use of oral contraception women should have been stable on the same pill for a minimum of 3 months before taking study treatment.
6. Fertile males, defined as all males physiologically capable of conceiving offspring **UNLESS** they use a condom during intercourse while taking the study medication and for 1 week after stopping study medication and should not father a child in this period. A condom is required to be used also by vasectomized men in order to prevent delivery of the drug via seminal fluid.
7. Patients who have been treated with mitotane during the last 6 months prior to Visit 1.
8. Patients with compression of the optic chiasm, in order to exclude patients with a tumor causing chiasmatal compression requiring surgery.

9. Patients who have a known inherited syndrome as the cause for hormone over secretion (i.e. Carney Complex, McCune-Albright syndrome, MEN-1, AIP).
10. Patients with Cushing's syndrome due to ectopic ACTH secretion or adrenal Cushing's syndrome.
11. Patients with pseudo-Cushing's syndrome (for patients with a mean UFC < 3xULN further testing to rule out this condition will be required unless Cushing's disease is confirmed by histopathology.) At least 2 of 3 tests should be abnormal in order to exclude pseudo-Cushing's: low-dose dexamethasone suppression test, dexamethasone-CRH test or late salivary or serum cortisol.
12. Patients with renal impairment (estimated creatinine clearance < 60 ml/min by the MDRD formula), serum creatinine >2.0 X ULN.
13. Patients who are not biochemically euthyroid.
14. Patients who have undergone major surgery within 1 month prior to screening.
15. Diabetic patients with poorly controlled diabetes as evidenced by HbA_{1c} > 9 %.
16. Patients who have congestive heart failure (NYHA Class III or IV), unstable angina, sustained ventricular tachycardia, clinically significant bradycardia, advanced heart block, history of acute MI less than one year prior to study entry or clinically significant impairment in cardiovascular function.
17. Patients with liver disease such as cirrhosis, chronic active hepatitis, or chronic persistent hepatitis, or patients with ALT/AST more than 3 X ULN, serum bilirubin >2.0 X ULN.
18. Patients who have any current or prior medical condition that can interfere with the conduct of the study or the evaluation of its results in the opinion of the investigator or the sponsor's medical monitor.
19. Patients who have a history of alcohol or drug abuse in the 6 month period prior to treatment.
20. Patients with a history of non-compliance to medical regimens or who are considered potentially unreliable or will be unable to complete the entire study.
21. Patients who have received pituitary irradiation within five years prior to Visit 1.
22. Patients with risk factors for QTc prolongation or Torsade de Pointes, i.e. patients with a baseline QTcF > 470ms, hypokalemia, hyperkalemia, hypocalcaemia, hypomagnesaemia, uncontrolled hypothyroidism, personal or family history of long QT syndrome, or concomitant medications known to prolong the QT interval.

[figure not shown]
No additional exclusions may be applied by the investigator, in order to ensure that the study population will be representative of all eligible patients.

5 Treatment

